3.4 Study area and setting

1. This study will be conducted in close rooms at educational hospital, public hospital and private dental clinic. Humidity and temperature will be recorded at the beginning, measuring particles oral bacteria and fungus will be performed 15 minutes before and approximately 15 minutes during scaling and prophylaxes procedure in two opposite quadrants in left side. Additionally 5 minutes will require between two interval to allow cleaning process of filter in Digital dust monitor. Microbial sampler devices will be distributed at several locations in room, three microbial air sampler devices around patient, at 8 o'clock position, 1 o'clock position and 4 o'clock. Another device that will be placed near to air condition and one agar media on the floor to control another microbial agents that could be arising from A.C.. Intervention devices that will be used is EOS where being place on left side of patent to allow comfortable movement of hygienist and suction cone will be away from patient mouth from 10 -15 cm based on manufacture instruction.

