3.8 Sampling technique

Multiple stage stratified random sampling at place level then subject randomly assign from schedule appointment using simple random sampling. Last stage, Simple random sampling of 40 subject at each 4 groups using computer-generated random numbers.

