3.10 Variables and Data collection

Measurement devices

2. Digital dust monitor

Particles matter will be measured using Digital dust monitor (model 3443, KANOMAX.USA INC., made in Japan). This device measure particle size that range from 0.1 to 10 Mm using light scattering method (semiconductor laser radiation light source) with flow rate 1 L/min. air is collect through a filter which is built-in in order to eliminate coarse particles. Filter is reusable and it needs approximately 5 minutes cleaning time depending on environment. Minimum, maximum, and average concentration result show among measurement time. Calibration of device will be performed according to manufacture instruction.

3. Microbial air sampler device (sampl'air ASE)

Is considered as active air sampler method which used to collect microorganism onto solid media with flow rate 100 L/ min. Positive hole conversion table should be used in order to counting colony; colony forming units per volume of air (CFU m⁻³).

In this study a specific agar media will be used to collect oral bacteria and fungus.

Outcome variable

Particle count level (difference in PN count[ΔPN ;post-test – pre-test , counts/ m³])
(continuous variable)

Average of oral bacterial concentration before and during procedure

Average of fungus concentration before and during procedure

Microbial air concentration including bacteria and fungus before and during procedure (floor and near to A.C)

Explanatory variable

Categorical variable

Place ,intervention groups, order of patient ,gender and supragingival calculus (mild, moderate, heavy) ,

Continuous variable

time of procedure that staring from the beginning of scaling until finishing of scaling (in minutes), time on day (morning, afternoon), age, year experience of hygienist, distance of room, humidity, and room temperature.

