3.11 Statistical consideration

All continuous variables will be express as mean and stander deviation

All categorical variables will be described as frequency and percentage

Difference between baseline and during of procedure measurement intended for particle, oral bacteria, fungus and microbial air concentration will be calculating using pairwise t test.

Difference between each categorical groups and particle, oral bacterial, fungus, and microbial air concentration will be tested using two way ANOVA test or one way ANOVA test

Strength and direction of association between particle count levels and time of procedure will be tested using correlation test

Multiple linear regression model will be built to predict particles count level with entrance value of 0.01 and exit value 0.101. Confidence level of 95% will be computed and p-value less than 0.05 will be considered as significant.

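### The between-group ANOVA leaves out the pre-procedure reading as a covariate and may leave out place, so group comparisons can be less precise than the collected data allow

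*Combined protocol and SAP*

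**What the plan says.** Section 3.4 provides a baseline for every subject: "measuring particles oral bacteria and fungus will be performed 15 minutes before and approximately 15 minutes during scaling". It places "three microbial air sampler devices around patient", with further sampling near the air conditioner and on the floor.

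Section 3.8 describes "Multiple stage stratified random sampling at place level". The Abstract gives 40 subjects in each of three places, and section 3.7 gives a total of 120.

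Section 3.10 defines the particle outcome as a change, "Particle count level (difference in PN count", taken as the later reading minus the earlier one. The bacterial outcome is "Average of oral bacterial concentration before and during procedure", and the fungal outcome has the same form. Place and intervention group are listed as categorical explanatory variables. The continuous list ends with "age, year experience of hygienist, distance of room, humidity, and room temperature". The pre-procedure reading is in neither list.

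Section 3.11 uses a paired t test for baseline against during. Each outcome is then compared across the categorical groups, which "will be tested using two way ANOVA test or one way ANOVA test". For particles only, "Multiple linear regression model will be built to predict particles count level with entrance value of 0.01 and exit value 0.101".

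**The concern.** Objectives 3 and 4 (section 2.3) are comparisons between groups, so the between-group model is the one that matters most. Three things about it are open or missing.

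- **Baseline.** No between-group model has the pre-procedure reading as a covariate. Subtracting it, as for particles, fixes its slope at 1. If the true slope is different, subtraction leaves avoidable noise in the comparison.
- **Response for bacteria and fungus.** The outcome wording fits the during value, the change, or one mean pooled over both periods. Two analysts could follow the plan and test different quantities.
- **Place.** A one-way ANOVA on group is permitted and would leave differences between places in the error term. A two-way ANOVA may include place, but the plan does not say so.

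The multiple regression does not close these gaps. It covers particles only, the pre-procedure reading is not among its listed candidates, and selection by entry and exit values does not guarantee that place stays in.

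At stake is the width of the confidence intervals for the group differences. The plan gives no power calculation that would show precision to spare.

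**Working it through.** **Inputs.** From the documents: 120 subjects, four groups, three places of 40 (3 × 40 = 120). Equal groups would be 30 each, or 10 per group per place. Section 3.8 can also be read as 40 in each of four groups, which is 160 and conflicts with 120; the conclusion is the same at 30 or 40 per group. Assumed, because the documents are silent: r, the pre/during correlation; k, the during/pre SD ratio; p, the share of response variance due to place. There is no power or precision figure in the plan to reproduce.

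**Step 1. Particles: change score against ANCOVA.** Set the pre-procedure SD to 1 and the during SD to k, with a common slope.

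- Change-score variance: k² + 1 − 2rk
- ANCOVA variance: k²(1 − r²)
- Difference: (1 − rk)², which is never negative
- Share saved: (1 − rk)² / (k² + 1 − 2rk)

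Example, r = 0.3 and k = 1: 0.49 / 1.4 = 0.35.

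| Share saved | r = 0.3 | r = 0.5 | r = 0.7 |
|---|---|---|---|
| k = 1 | 35% | 25% | 15% |
| k = 1.5 | 13% | 4% | 0.2% |
| k = 2 | 4% | 0% | 7% |

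The saving is zero whenever rk = 1, that is, when the true slope is 1. A simulation (120 subjects, 10 per group per place, place in both models, 20,000 runs, group A against C) gave 34/25/14%, 12/3/−0.9% and 3/−1.1/7% for the three rows. The small negative values are the cost of estimating a slope that was not needed.

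**Step 2. Bacteria and fungus: during value alone against ANCOVA.** The variance falls from k² to k²(1 − r²), so the share saved is r² for any k: 9%, 25% and 49% at r = 0.3, 0.5 and 0.7. It is 1% at r = 0.1. The simulation gave 8%, 23–25% and 48–49% at the three main values. If the change is analysed instead, Step 1 applies. If a mean pooled over both periods is analysed, the group difference is halved, because the pre-procedure reading cannot carry a device effect.

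**Step 3. Place.** Leaving out a balanced factor that explains share p multiplies the error variance by 1/(1 − p): 1.053, 1.111 and 1.250 for p = 0.05, 0.10 and 0.20. For particles p is probably at the low end, because subtraction already removes stable background differences between places.

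**Step 4. What this means for detection.** With 30 per group, two-sided 5% and 80% power, the detectable pairwise difference is (1.96 + 0.84) × √(2v/30). At r = 0.5 and k = 1, v = 1 for the change score or the during value, giving 0.72 SD; v = 0.75 for ANCOVA, giving 0.63 SD. With 40 per group the figures are 0.63 and 0.54 SD.

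A simulated four-group F test (1,500 runs; shifts 0, −0.3, −0.3, −0.6 SD; r = 0.5; k = 1; place 20% of change-score variance, acting on the during value only) gave power of 34% for one-way ANOVA on change, 47% with place added and 59% for ANCOVA with place. With no group effect, the one-way test rejected 2.7% of the time against a nominal 5%. Leaving out a balanced stratum is therefore conservative.

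**Step 5. Cost of the covariate.** Error degrees of freedom fall from 120 − 4 = 116 (one-way) to 120 − 4 − 2 − 1 = 113. The 95% t critical value moves from 1.9806 to 1.9812. Estimating an unneeded slope inflates the variance of a group contrast by about 1/112, or 0.9%.

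**The case against.** The best counter-argument concerns particles. If the during reading is room background plus independent aerosol from the procedure, which is natural in a closed room, the slope is 1 and the change score is already as good as ANCOVA. Under that model k = 1 would require r = 1, so the 35/25/15% row cannot arise, and the power figures in Step 4, which use k = 1, are a favourable case. This stands: the gain for particles may be nil.

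Place and group are both listed as categorical variables, so a group-by-place two-way ANOVA is a fair reading. This also stands: place is left open rather than definitely omitted. But the choice between the two tests is not fixed in advance, and neither option includes the baseline.

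For bacteria and fungus, the sentence just before the ANOVA concerns the baseline-to-during difference, so a change-score reading is possible. The r² savings then do not apply. That makes the size uncertain and confirms that the response needs defining.

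Two further limits are accepted. The statement that ANCOVA is never less precise assumes a common slope across groups, which suction devices could alter. The simulations assume balance within place, which simple random allocation does not guarantee. Neither makes the planned ANOVA preferable.

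**Conclusion.** The concern holds as a loss of precision. Randomised comparisons by change score or by ANOVA remain valid.

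The firmest part needs no assumed figure: the plan does not fix the ANOVA factors or the bacterial and fungal response, and it names no baseline covariate for any outcome. The size does rest on assumed r, k and p. For particles it runs from a loss of about 1% to a saving of 35% of variance, with 0% to 13% at k = 1.5 or 2. For bacteria and fungus it is 9% to 49% over r = 0.3 to 0.7 if the during value alone is analysed, and close to nothing if r is near zero. For place it is 5% to 25% extra error variance if a one-way model is used. Because the change is nearly free, it is worth making even though the gain is uncertain.

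**What to change.** In section 3.11, replace the open choice of ANOVA for the group comparison with one pre-specified ANCOVA per outcome. The factors are intervention group and place, both kept whatever their p-values. The covariate is the same subject's pre-procedure reading of that outcome.

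- **Particles:** the response may stay as the change score. With the pre-procedure reading as covariate, it gives the same group effect as modelling the during reading.
- **Bacteria and fungus:** the response is the during-procedure value.
- **Microbial air (floor and air conditioner):** the same form, with its own pre-procedure reading.

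Report adjusted group differences with 95% confidence intervals. A log-scale analysis can be added as a sensitivity analysis. The selection-based regression should be kept separate from this comparison.

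In section 3.10, define the bacterial and fungal outcomes as the mean over the three samplers around the patient, given separately for before and during.

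The cost is a change of wording, with no new data or visits. Three error degrees of freedom are spent relative to the one-way model. If the true slope is 1, the particle comparison loses about 1% in variance.

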Effectiveness of Extra- oral Suction Comparing to Other Suction in Reducing Particles Matter and Bioaerosol in Dental Clinic, Randomized Clinical Trial.

NCT05848245

September 15, 2022

[name]

Supervised by

[name], [name], [name]

Content table

.1	Abstract in English	3
.2	Introduction	4
	Background 3.1	4
	Rational of research 3.2	5
	Objective 3.3	5
	MATERIAL AND METHODS .4	5
	Study design 4.1	5
	Intervention devices 4.2	5
	Intervention groups 4.3	6
	Study area and setting 4.4	6
	Assessment 4.5	6
	Study participants 4.6	7
	Sample size 4.7	7
	Sampling technique 4.8	7
	Inclusion and exclusion criteria 4.9	7
	Variables and Data collection 4.10	7
	Statistical consideration 4.11	9
	Ethical consideration 4.12	9
	Limitation and strength 4.13	9
	Devices and setting figure .5	10
.6	References	12

1. Abstract in English

Aerosol particles generated when using dental instrument such as ultrasonic and high air driven handpieces, this aerosol is mixture of blood, saliva, infectious agents, and dental materials. Inhaler dust that range between PM2.5 to PM10 could transferred to the human lung's terminal bronchioles and alveoli that cause a harm effect.

The aim of this study to assess the effectiveness of different dental suction devices that could be contributed to decrease risk of particles count, Bacterial and fungal that arising from patient mouth to indoor air dental clinic

This is a randomized clinical trial will be conducted in three different places: educational hospital, public hospital, and private clinic. In each place 40 subject will be recruited. Measurement including particles count and microorganism will be taken before 15 minutes and during of scaling and prophylaxis procedure to measure particles count, oral bacteria, fungus, and microbial air. In this study will be compared between four intervention groups; Group A with high and low suction only, Group B using dry shield suction and low section, Group C using extra-oral suction with high and low suction, and Group D using dry shield suction and extra-oral suction and low section. Difference between each categorical groups and particle, oral bacterial, fungus, and microbial air concentration will be tested using two-way ANOVA test or one way ANOVA test. Statistical analysis will be carried using STATA version 13.

2. Introduction

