3.7 Sample size

Total sample will be 120 subjects.

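### The correlation of particle level with procedure time names no adjustment for suction group or place, so it mixes within-stratum and between-stratum association; a version adjusted for both would be more informative at almost no cost.

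*Combined protocol and SAP*

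**What the plan says.** Section 3.11 (Statistical consideration) plans this analysis in one sentence: "Strength and direction of association between particle count levels and time of procedure will be tested using correlation test". The type of coefficient, any stratification and any adjustment are left open. The same section judges results at 0.05 and asks for 95% confidence.

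Section 3.10 (Variables and Data collection) defines the outcome as a change score, "Particle count level (difference in PN count[ΔPN ;post-test – pre-test , counts/ m³", and the time variable as "time of procedure that staring from the beginning of scaling until finishing of scaling (in minutes". Scaling time is therefore observed after allocation. The same section lists the categorical explanatory variables, "Place ,intervention groups, order of patient ,gender and supragingival calculus (mild, moderate, heavy", without linking any of them to the correlation.

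The data are structured. The Abstract names "three different places: educational hospital, public hospital, and private clinic", states "In this study will be compared between four intervention groups", and adds "In each place 40 subject will be recruited". Section 3.7 gives "Total sample will be 120 subjects".

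Section 3.11 also plans a multiple linear regression for particle count level, with an entry value of 0.01 and an exit value of 0.101. It does not say which terms stay in the model regardless of their p-values.

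**The concern.** Particle level is expected to differ by suction group, since that is the purpose of the trial. Place is not randomised. Hygienist experience, room and calculus are all on the protocol's own list of explanatory variables and may differ between places. Scaling time may differ by place for similar reasons. Randomisation does not guarantee that it is equal across groups either, because the device in use could change it.

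A correlation taken across these strata can therefore be weaker than the association seen among patients treated in the same place with the same suction. It can also be non-zero when there is no such association. Because the result carries a significance test, readers are likely to take it as showing that longer scaling does, or does not, mean more exposure.

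**Working it through.** **Inputs.** Three places, four groups, 40 subjects per place and 120 in total (Abstract; section 3.7). The total reproduces as 3 × 40 = 120. No power, SD, mean or expected correlation is given for this analysis. Assumptions: ten subjects in each of the 12 place-by-group cells, a two-sided test at 0.05, and within-stratum SDs set to 1 for both time and ΔPN. With N = 120, |r| must exceed 0.179 to be significant.

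**Formula.** Let ρ be the within-stratum correlation, B_t and B_y the between-stratum variances of time and ΔPN, and B_ty their between-stratum covariance. Then

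marginal r = (ρ + B_ty) / √[(1 + B_t)(1 + B_y)].

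Three equally spaced places with step d have between-stratum variance 2d²/3. Four equally spaced groups with step g have variance 1.25g². Rejection rates below come from simulation (20,000 runs per scenario).

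**1. Groups differ on particles only, time balanced, ρ = 0.30.** Here B_t = B_ty = 0.
- g = 0.5: 0.30/√1.3125 = 0.26; power 82%.
- g = 1: 0.30/√2.25 = 0.20; power 59%.

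The test adjusted for group and place has power of about 91% in both cases. If ρ = 0, the unadjusted test keeps its 5% error rate in this scenario (checked at g = 0.5), so the effect is dilution and not a false signal.

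**2. Places shift in the same direction on both variables, ρ = 0.** r = (2d²/3)/(1 + 2d²/3).

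| Step d (SD) | 2d²/3 | Marginal r | Rejection rate |
|---|---|---|---|
| 0.25 | 0.042 | 0.04 | 7% |
| 0.5 | 0.167 | 0.14 | 35% |
| 0.75 | 0.375 | 0.27 | 87% |
| 1 | 0.667 | 0.40 | 99.8% |

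An observed r of 0.14 has p = 0.12, so at 0.5 SD the typical trial would not reach significance. The adjusted test rejects in about 5% of trials in every row.

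**3. Places shift in opposite directions, ρ = 0.30.** At d = 0.5, r = (0.30 − 0.167)/1.167 = 0.11, with power 22%, against about 91% adjusted.

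**4. The two dryshield groups (B and D) run s SD longer and s SD lower in particles.** The between-group variance is 0.25s² for each variable and the covariance is −0.25s².
- s = 0.5: with ρ = 0, r = −0.0625/1.0625 = −0.06 (p = 0.52); with ρ = 0.30, r = 0.2375/1.0625 = 0.22.
- s = 1: with ρ = 0, r = −0.25/1.25 = −0.20 (p = 0.03); with ρ = 0.30, r = 0.05/1.25 = 0.04.

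**5. Does the planned regression cover this?** Suppose group and place were already in the model and ρ = 0.30. Time would then reach p < 0.01 in about 76% of simulated trials, so it would miss the entry threshold in about one in four. Nothing keeps group and place in the model either.

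**6. Cost of adjusting.** Three group terms and two place terms take 118 degrees of freedom to 113. With no shifts at all and ρ = 0.30, simulated power is 0.906 adjusted against 0.917 unadjusted.

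**The case against.** The strongest reply is that the plan promises only the strength and direction of an association, and a marginal correlation does estimate that. A simple correlation followed by a multiple regression is a common descriptive sequence. Procedure time, place and group all appear among the explanatory variables, so the regression may give the adjusted slope anyway. None of the four objectives in section 2.3 concerns procedure time.

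Most of this stands. A reader might infer that the plan commits to a pooled test over all subjects and so yields a wrong estimate. The documents do not support that. Pooling is the plain reading of a sentence that names no strata, but it is not stated, and the marginal coefficient is less informative rather than invalid. The regression weakens the concern without removing it, because p-value selection does not guarantee that time, group and place appear in it together.

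The design also makes large shifts less likely. Section 3.4 limits scaling to two quadrants and about 15 minutes, and a change score removes stable background differences between rooms. Neither feature rules out place effects: if times are tightly clustered, a small difference in minutes can still be large in SD units. Nothing in the documents says that dryshield lengthens scaling, so step 4 of the working is only an illustration.

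**Conclusion.** The point holds as a cheap improvement to a secondary analysis. Dilution needs only a group effect on particles, which is the trial's own hypothesis, and it is modest: 0.30 becomes 0.26 or 0.20 for steps of 0.5 or 1 SD. A false association needs both variables to shift across strata. It is negligible at place steps of 0.25 SD (r = 0.04), moderate at 0.5 SD (0.14) and large only at 1 SD (0.40), where the outer places differ by 2 SD on both variables.

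All of these figures rest on assumed shifts and an assumed ρ. A reader might infer that a spurious correlation near 0.40 is to be expected, or that the comparison of suction groups is compromised. The documents give no means or SDs to support the first, and this analysis plays no part in the second.

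**What to change.** In section 3.11, replace the correlation sentence with one that reports the partial correlation of ΔPN with procedure time, or the slope of ΔPN on procedure time, with suction group and place forced into the model, and with a 95% CI. Label it a secondary descriptive result. State that it may still carry confounding by other factors, such as calculus severity, which could affect both scaling time and particles.

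Keep procedure time out of the model that estimates the group effect, because it arises after randomisation and may be affected by the device.

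Adjustment is preferable to separate correlations in each of the 12 cells. With ten subjects per cell, |r| would have to exceed 0.63 to be significant.

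The cost is five degrees of freedom out of 118 and one line of text. No new data are needed, because all the variables are already to be collected.

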2.3 Objective

1. Measure particles, bacteria and fungus that arising from patient's mouth in each group.
2. Evaluate health exposure risk for each group to baseline reading (pre-test).
3. Compare health exposure risk for each group to standard group (Group A)
4. Compare health exposure risk between each of the following groups A, B , C and D.

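### The particle-count prediction regression selects terms by p-value with intervention group and place unprotected, so the only multi-covariate model can drop or pool the randomised arms

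*Combined protocol and SAP*

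**What the plan says.** Section 3.11 (Statistical consideration) plans paired t tests against baseline, a comparison across groups, a correlation of particle count with procedure time, and a regression. On the group comparison it says that differences "will be tested using two way ANOVA test or one way ANOVA test". The abstract also gives this comparison to ANOVA and does not mention the regression.

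On the regression it says: "Multiple linear regression model will be built to predict particles count level with entrance value of 0.01 and exit value 0.101". It then adds: "Confidence level of 95% will be computed and p-value less than 0.05 will be considered as significant".

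Section 3.10 defines the particle outcome as the change from pre-test to post-test. It lists five categorical explanatory variables, beginning "Place ,intervention groups, order of patient ,gender and supragingival calculus", and seven under the continuous heading, 12 in all. Intervention group stands in that list on the same footing as gender or humidity. The list serves the whole study; the text does not say that all 12 are candidates for the regression.

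No section says that group or place is forced into the regression, that the group indicators enter or leave together, which way the search runs, or which analysis is primary.

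**The concern.** Objectives 3 and 4 in section 2.3 compare each group with Group A and the groups with one another. The regression is the only planned analysis that can adjust for several covariates at once; the ANOVA has at most two factors, and the second is not named. Followed as written, the selection rule decides from the data whether the randomised factor appears in that model.

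Three things can follow. Group may be absent, so no adjusted device effect is reported. If indicators are selected one at a time, an omitted arm joins the reference arm and the remaining coefficients no longer compare with Group A. If group is kept because its p-value was small, its estimate is on average too large. A regression without group, or with merged arms, could then appear beside a significant ANOVA with no stated rule for reading the two together.

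**Working it through.** **No plan figure to reproduce.** The plan gives no effect size, SD or power for particle count. Every result below rests on assumed effects, shown as a range.

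**Inputs from the documents.** Total 120 (section 3.7), 40 per place in three places (abstract), four groups (section 3.3), entry 0.01, exit 0.101, significance 0.05 (section 3.11), 12 explanatory variables (section 3.10).

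**Assumptions.** Equal arms, 120/4 = 30. Within-group SD 1. Means A = 0, B = −d/2, C = D = −d, with d = 0.5, 0.8, 1.2. All 12 variables are candidates: place 2 df, group 3, order of patient 1, gender 1, calculus 2, plus 7 = 16 df. Case N has no prognostic covariates. In case P, place and humidity together explain 40% of within-group variance.

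**Step 1: group test alone.** The grand mean is −0.625d. Squared deviations sum to (0.390625 + 0.015625 + 0.140625 + 0.140625)d² = 0.6875d². Non-centrality is 30 × 0.6875d² = 20.625d², that is 5.16, 13.2 and 29.7. From the non-central F(3,116):

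| d | P(p<0.05) | P(p<0.01) | P(p<0.10) | 0.05 minus 0.01 |
|---|---|---|---|---|
| 0.5 | 0.439 | 0.217 | 0.570 | 0.222 |
| 0.8 | 0.864 | 0.681 | 0.923 | 0.183 |
| 1.2 | 0.998 | 0.986 | 0.999 | 0.012 |

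With no other useful covariate, group therefore fails an entry test at 0.01 in about 78%, 32% and 1% of trials. The last column is the chance that group is significant at 0.05 but fails 0.01. Section 3.8 can be read as 40 per group ("Simple random sampling of 40 subject at each 4 groups using computer-generated random numbers"); that column then becomes 0.242, 0.103 and 0.001.

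**Step 2: full selection, group as one 3-df term.** Simulation with exit 0.101, 4000 runs per setting, Monte Carlo error up to 0.8 points. Entries are for d = 0.5 / 0.8 / 1.2.

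| Search | Case | Group absent, % | Significant in one-way ANOVA but absent, % | C−A estimate when kept, multiple of truth |
|---|---|---|---|---|
| Forward 0.01 | N | 78 / 34 / 2 | 22 / 19 / 1.5 | 1.55 / 1.13 / 1.01 |
| Forward 0.01 | P | 59 / 8 / 0.1 | 14 / 3 / 0.1 | 1.29 / 1.04 / 1.00 |
| Backward 0.101 or forward 0.10 | N | 42–44 / 9 / 0.1 | at most 0.3 | 1.27–1.29 / 1.03–1.04 / 1.00 |
| Backward 0.101 or forward 0.10 | P | 21–23 / 1 / 0 | at most 2.3 | 1.12–1.13 / 1.01 / 1.00 |

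Coverage of the 95% interval when group is kept falls to 0.86 only for forward 0.01 at d = 0.5 in case N. Elsewhere it is 0.93–0.96.

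**Step 3: indicators selected singly, with A as reference.** If B is dropped and C and D stay, the reference is A and B together with mean −d/4, so the C coefficient targets −d + d/4 = −0.75d. If only C stays, the reference mean is −(0 + 0.5 + 1)d/3 = −0.5d and the coefficient targets −0.5d. In simulation (2000 runs) at d = 0.8, only one or two of the three indicators are kept in 37% (forward 0.01), 56% (forward 0.10) and 52% (backward) in case N, and in 55%, 41% and 38% in case P. When C is in such a model, its coefficient averages 0.97, 0.82 and 0.81 of the true C−A difference (N), and 0.85, 0.78 and 0.78 (P). At d = 0.5 in case N it averages 1.37, 1.11 and 1.08, so the error can go either way.

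**Step 4: the alternative.** A fixed model with group and place (plus humidity in case P) averages 0.99–1.01 of the truth over all trials, with coverage 0.95. Looked at only when group has p<0.05, it too overstates: 1.37 / 1.06 / 1.00 (N) and 1.17 / 1.01 / 1.00 (P).

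**The case against.** The strongest reply is that the plan already separates the tasks: ANOVA for devices, regression for predictors. The abstract and section 3.11 support this, and no objective asks for prediction or adjustment. This stands. A reader might infer that the trial could lose its test of the devices, but the documents do not support that, because the ANOVA tests group without selection. What remains is that nothing is labelled primary and the regression has no rule for group.

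Second, the large figures need forward selection, 0.01 taken literally and a small to moderate effect. This also stands. With entry at 0.10 or a backward search, a group significant in the ANOVA is almost never dropped when handled as one term. At d = 1.2 omission is rare under every reading. Singly selected indicators are the exception: at d = 1.2, one or two of three are kept in 54, 27 and 26% (N) and 38, 11 and 10% (P) for forward 0.01, forward 0.10 and backward.

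Third, much of the inflation is ordinary significance filtering, which step 4 shows for the fixed model as well. That is right. The gain from a fixed model is that its group coefficient is reported whatever the p-value.

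Fourth, entry at 0.01 beside significance at 0.05 might be read as a contradiction. It is not, since the two thresholds do different jobs. A p-value at one step can also change as other terms enter.

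**Conclusion.** The point holds in a limited form. The stated selection rule leaves group and place unprotected in the only multi-covariate model, which can omit the randomised factor or merge an arm with the reference. It affects that model alone, and does harm only if its group coefficient, or the absence of one, is read as evidence about the devices.

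The size depends on an effect the documents do not give, on the unstated search direction and on how group is coded; it also assumes that group is a candidate and A the reference. A reader might infer that the retained group coefficient is generally inflated. The figures do not support that: as one term, overstatement is material only for small to moderate effects, mainly at entry 0.01. Nor can the documents settle whether 0.01 is a slip for 0.10. The closeness of 0.10 to the exit value 0.101 makes it plausible, no more. Severity is minor to moderate.

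**What to change.** - Name the ANOVA on group and place as the main group comparison, and the regression as supportive. Without interaction, that ANOVA is the same model as a regression on group and place, so the two can be aligned.
- Report adjusted group effects on the change in particle count from one regression without entry or exit values. It should always contain group (three indicators together, Group A as reference) and place, plus a short covariate list fixed in advance. Place belongs because section 3.8 describes "Multiple stage stratified random sampling at place level" and the sites use different rooms.
- Leave procedure time out of this model, because it is measured after randomisation.
- Label any stepwise predictor search exploratory, force in group and place, and state its direction.
- Confirm whether the entry value 0.01 was meant to be 0.10.

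The change needs SAP wording only, with no new data or participants. The cost is that the sponsor must choose the covariates in advance and fewer predictors are reported.
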